4 STUDY OBJECTIVES

The goal of this multicenter clinical observation study is to validate the short-, mid- and long-term outcome efficacy and safety of the POLARSTEM.

CONFIDENTIAL AND PROPRIETARY

This document contains information that is confidential and proprietary to Smith & Nephew PLC and Smith & Nephew, Inc. and is intended for use only by Smith+Nephew and its manufacturer. It shall not be reproduced or copied in whole or in part, nor shall the contents be disclosed by any means without prior written permission from Smith+Nephew, nor shall anyone make any use of it that is contrary to the expressed or implied wishes of Smith+Nephew.

Statistical Analysis Plan

Multicenter Clinical Observation Using the Cementless Version of the
POLARSTEM™

Number: D10070
ST: 1133
Version: 1.0, 30-Nov-2021
Page: 6 of 19

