7 STATISTICAL ANALYSIS

7.1 General

Smith & Nephew's Global Biostatistics group will conduct the statistical analysis for this study. Unless otherwise stated, all significance tests and hypothesis testing will be two-sided, performed at the 5% significance level. Resulting p-values will be quoted and 95% two-sided confidence intervals will be generated where appropriate. All p-values will be rounded to three decimal places, p-values less than 0.001 will be presented as '<0.001' in all tables.

Baseline data, outcome variables and adverse events will be summarized according to the nature of the variable. Categorical and ordinal variables will be summarized with frequencies and percentages. Continuous variables will be summarized with the following summary statistics: number of observations, mean, median, standard deviation, minimum and maximum values. The outcome variables will be summarized for all recorded time points.

Appropriate parametric and/or non-parametric analyses will be chosen for statistical analysis. The analysis of continuous variables will be done using a paired-sample t-test if appropriate, to test for differences between the baseline and end of study outcomes. The Wilcoxon rank-sum tests will be explored if the data is non-normal.

If data allows, Kaplan-Meier estimates will be calculated for the survival data otherwise only the survival proportion with a 95% confidence interval will be reported..

All analyses will be performed in SAS version 9.4 (or later).

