7.2 Analysis Populations

All subjects who provide informed consent are considered study participants. Study populations are defined as follows:

CONFIDENTIAL AND PROPRIETARY

This document contains information that is confidential and proprietary to Smith & Nephew PLC and Smith & Nephew, Inc. and is intended for use only by Smith+Nephew and its manufacturer. It shall not be reproduced or copied in whole or in part, nor shall the contents be disclosed by any means without prior written permission from Smith+Nephew, nor shall anyone make any use of it that is contrary to the expressed or implied wishes of Smith+Nephew.

Statistical Analysis Plan

Multicenter Clinical Observation Using the Cementless Version of the POLARSTEM™

Number: D10070
ST: 1133
Version: 1.0, 30-Nov-2021
Page: 9 of 19

- **Full analysis population (FAS)**, including all subjects that were included in the study, who received study treatment and attended at least one post baseline assessment.
- **Per protocol analysis population**, including all subjects in the full analysis population, have no significant protocol deviations and meet the inclusion/exclusion criteria.
- **Safety population**, including all subjects who have received study treatment.

Statistical analysis will be performed using each of the subject populations as follows: Analysis of primary, secondary and exploratory variables will be performed separately using both the FAS and the Per-Protocol Set. All safety analyses will utilise the Safety Population. Demographic characteristics will be summarized for each analysis population. Demographic characteristics will be summarized on a subject level. For bilateral subjects the data corresponding to the date of the hip's first enrolment into the study will be used.

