7.3 Handling of Missing, Incomplete and Repeat Data

Missing and incomplete data are usually due to lost to follow-up, revision, death and patient withdrawal. A complete accountability along with the explanation for lost-to-follow-up, death, revision, and withdrawn patients will be provided in the final study report and these subjects will be treated as censored at the date of lost-to-follow up in the survival analysis. The missing due to revision will be treated as device failure. A complete assessment of the informative/non-informative missing data will be performed. In case of missing outcome values at designated time points, the last observation carried forward (LOCF) method will be used.

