- ❖ **Withdrawn Subject:** A withdrawn subject will be considered as one who does not complete the study because of to loss to follow-up or the early termination or any other known reason.
- ❖ **Completed Subject:** This study has been terminated early, a subject will be considered as having completed the study if he/she completed the 10 year visit for the study prior to its termination.

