7.11 Analysis of Secondary Endpoints

- Harris Hip Score (HHS)

CONFIDENTIAL AND PROPRIETARY

This document contains information that is confidential and proprietary to Smith & Nephew PLC and Smith & Nephew, Inc. and is intended for use only by Smith+Nephew and its manufacturer. It shall not be reproduced or copied in whole or in part, nor shall the contents be disclosed by any means without prior written permission from Smith+Nephew, nor shall anyone make any use of it that is contrary to the expressed or implied wishes of Smith+Nephew.

Statistical Analysis Plan

Multicenter Clinical Observation Using the Cementless Version of the POLARSTEM™

Number: D10070
ST: 1133
Version: 1.0, 30-Nov-2021
Page: 17 of 19

- HOOS Score (Hip Dysfunction and Osteoarthritis Outcome Score), which includes the complete WOMAC Osteoarthritis Index
 - The different dimensions of and the overall HHS, and WOMAC from HOOS scores at all recorded time points and end of study will be summarized using mean, median, SD, minimum, and maximum. A paired sample t-test (or a non-parametric equivalent such as the Wilcoxon signed-rank test) will be used to test the difference between preoperative and postoperative scores.
- Radiological: At all recorded time points (from the perioperative through the 10 year postoperative follow-up), the following analyses would be carried out:
 - For general findings: At the acetabulum position, cranial migration (mm), medial migration (mm) and tilted angle would be summarized using descriptive characteristics for continuous variables; At the stem position, varus tilting, valgus tilting and sunken (mm) will be summarized using descriptive statistics for continuous variables; Integration in general/acetabulum, integration in general/stem and ectopic ossification will be summarized using descriptive statistics for categorical variables.
 - Within the cup and the stem (by zone): The number and percent of hips with osteolysis will be summarized; for seams (0mm, 1mm, 2mm &>2mm), atrophy (none, mild, moderate & severe) and hypertrophy (none, mild, moderate & severe) their frequencies (n) and percentages will be presented.

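### SAP 7.1 sets the paired baseline test at an undefined end of study and 7.11 names no test visit, so the HHS and WOMAC contrast can mix scores from 3 months to 10 years

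*SAP*

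**What the plan says.** Two parts of the SAP govern the comparison of scores with baseline.

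- **SAP 7.1 (General)** provides a paired t-test for continuous variables, where appropriate, "to test for differences between the baseline and end of study outcomes". This is the only postoperative time point that the SAP names for a baseline test.
- **SAP 7.11 (Secondary Endpoints)** first describes summaries: HHS and WOMAC "scores at all recorded time points and end of study will be summarized". The next sentence says that a paired t-test or a non-parametric equivalent "will be used to test the difference between preoperative and postoperative scores". It names no visit.

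Four other places decide what end of study can contain.

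- **SAP 3** schedules follow-up at 3 months and 1, 3, 5 and 10 years.
- **SAP 7.4**, on completed subjects: "This study has been terminated early, a subject will be considered as having completed the study if he/she completed the 10 year visit" before termination. The same section uses end of study as one of several subject-level stop dates for survival time, but does not define it for the scores.
- **SAP 7.2** admits to the full analysis set subjects "who received study treatment and attended at least one post baseline assessment".
- **SAP 7.3**: "In case of missing outcome values at designated time points, the last observation carried forward (LOCF) method will be used".

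The stated goal in SAP 4 is to "validate the short-, mid- and long-term outcome efficacy and safety of the POLARSTEM".

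**The concern.** The objective separates three horizons, so a test against baseline needs a stated horizon. End of study does not supply one. If the follow-up time behind the value varies between subjects, the resulting mean change and p-value describe none of the three horizons, yet they would naturally be read as the long-term result. For survival, SAP 7.10 reports at fixed times; the scores have no equivalent rule for their test.

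At stake is the interpretation of the long-term HHS and WOMAC result. If scores move between the earlier visits and year 10, in either direction, a mixed value dilutes that movement in proportion to the share of subjects without a 10-year score.

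**Working it through.** **1. What end of study can mean.** The recorded visits already include year 10, and SAP 7.11 lists end of study in addition to them. That points to something other than the 10-year visit, most naturally each subject's last assessment. The survival-time derivation in SAP 7.4 fits this reading. The definition of a completer, which is tied to the 10-year visit, leaves the other reading open.

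- *Last assessment.* One post-baseline visit suffices for the full analysis set, so the value may be a 3-month, 1-, 3-, 5- or 10-year score. Handling missing visits differently would not change this.
- *10-year visit.* SAP 7.3 fills a missing 10-year score with the last earlier one, so the same mixture results. On this reading it would disappear if missing scores were left missing.

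**2. The plan's own figure.** The only calculated number in the documents is the 150 implantations per group in protocol 2.2. The stated inputs give 100 / (1 − 0.30) = 142.9, so 143; and 150 × 0.70 = 105, which meets the target of 100. The figure of 150 looks rounded up. Nothing here depends on it; only the 30% drop-out is used below.

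**3. Share of values that predate 10 years.** Inputs: 225 subjects enrolled and implanted (SAP 7.15) and 30% drop-out over 10 years (protocol 2.2).

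- 225 × 0.30 = 67.5, about 68 subjects without a 10-year score.
- 225 − 68 = 157 with one.

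The further share lost to early termination is not given. An assumed total share of 10% to 70% corresponds to 22.5 to 157.5 subjects.

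**4. Effect on the mean.** Let f be the share without a 10-year score and d the mean difference between their last score and a 10-year score. Then

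shift in the end-of-study mean = f × d.

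The mean paired change shifts by the same amount, because each subject's baseline is unchanged. The values of d are assumptions.

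| f | d = 2 | d = 5 | d = 10 |
|---|---|---|---|
| 10% | 0.2 | 0.5 | 1.0 |
| 30% (protocol) | 0.6 | 1.5 | 3.0 |
| 50% | 1.0 | 2.5 | 5.0 |
| 70% | 1.4 | 3.5 | 7.0 |

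If the earlier scores are lower than 10-year scores, d is negative and the shift changes sign.

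**5. Mean follow-up behind the value at f = 30%.**

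- All earlier scores from year 5: 0.70 × 10 + 0.30 × 5 = 8.5 years.
- Earlier scores spread equally over the first four visits: 0.70 × 10 + 0.30 × (0.25 + 1 + 3 + 5)/4 = 7.7 years.

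**The case against.** The strongest reply is that this is a gap in wording. End of study may simply mean the 10-year visit, the 7.1 text is general and conditional, and the 7.11 test can be read as a test at each visit. Means at every recorded visit are planned, so the 5- and 10-year results will appear beside any end-of-study figure. The scores are secondary endpoints with no comparator, threshold or decision rule.

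Much of this stands. It limits the harm, and it rules out several stronger statements that a reader might infer:

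- *That the SAP defines end of study as the last visit.* It does not; that reading is an inference from where the term is placed.
- *That 7.11 sets the p-value at end of study.* The sentence quoted from 7.11 concerns descriptive summaries. The end-of-study test is in 7.1.
- *That the SAP reports subjects who missed year 10, or that every subject has a different follow-up time.* SAP 7.4 says only that "This study has been terminated early" and who counts as a completer. Completers share the nominal 10-year time.
- *That a late decline would be hidden.* The documents give no score means, and per-visit summaries are planned, although carried-forward scores can enter those too.

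The reply does not remove the point. Reading the term as the 10-year visit brings in SAP 7.3 and the same mixture. The per-visit summaries do not settle which contrast is tested.

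**Conclusion.** The point holds in this form: the baseline test in SAP 7.1 is set at a time not defined for the scores, 7.11 names no test visit, and on either reading the plan as written mixes follow-up times wherever a subject lacks a 10-year score. This is more than missing detail, because the resulting contrast matches none of the horizons in the objective.

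At the protocol's 30% drop-out, about 68 of 225 values would predate year 10. The shift in the mean would be 0.6 to 3.0 points for an assumed difference of 2 to 10 points. Only the 30% and the 225 come from the documents, and 30% is a planning figure rather than an observed one. The true size and direction cannot be established.

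**What to change.** - In SAP 7.1 and 7.11, name the 10-year visit, on observed scores, as the long-term paired contrast for HHS and WOMAC.
- Report the same paired change with its 95% confidence interval at 3 months and 1, 3 and 5 years, each on the scores observed at that visit.
- Keep an end-of-study summary only if it is defined (for example, last available postoperative score), labelled supportive, and shown with the distribution of follow-up times behind it. It need not be deleted.
- State how 10-year visits outside the protocol's 120–123 month window are treated. Excluding them is not necessary for this fix.

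The change is to SAP wording only. The cost is fewer pairs in the long-term test: about 157 at 30% drop-out, fewer if termination removed more, against at most 225. At two-sided 5% and 80% power, the detectable standardised change goes from 2.80/√225 = 0.187 to 2.80/√157 = 0.223. Subjects with a 10-year score may also differ from those without one, so this possible completer selection should be stated beside the result.

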7.12 Analysis of Exploratory Endpoints

Not Applicable.

CONFIDENTIAL AND PROPRIETARY

This document contains information that is confidential and proprietary to Smith & Nephew PLC and Smith & Nephew, Inc. and is intended for use only by Smith+Nephew and its manufacturer. It shall not be reproduced or copied in whole or in part, nor shall the contents be disclosed by any means without prior written permission from Smith+Nephew, nor shall anyone make any use of it that is contrary to the expressed or implied wishes of Smith+Nephew.

Statistical Analysis Plan

Multicenter Clinical Observation Using the Cementless Version of the POLARSTEM™

Number: D10070
ST: 1133
Version: 1.0, 30-Nov-2021
Page: 18 of 19

7.13 Analysis of Safety Endpoints

- Intra- and perioperative implant-related “Adverse Events” (AE) and complications until discharge will be summarised
- Postoperative AE up to 10 years after the surgery
 - Adverse Events (as defined in Safety Reporting) – All adverse events will be tabulated classified by seriousness, relationship to the study device and given by frequency and percentages.

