2.2 Sample size consideration

Sample size estimations have been made on the assumption that for a valid statistical data analysis according to Kaplan-Meier, at least 100 implants surviving 10 years are necessary. Over a period of 10 years, a drop-out rate of 30% should be considered. Therefore, 150 initial implantations are needed in each group.

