3.4 Complications/adverse events/lost-to follow-up

Complications and adverse events are noted at each follow-up interval. For completed observations due to death of the patient, explantation of the device or patient's address unknown the latest status will be recorded as an endpoint. Patients will be considered lost to follow-up after they have missed two visits and all attempts to locate and evaluate them have failed. Patients who refuse to attend follow-up or patients unable to attend follow-up will be assessed by telephone if possible. Minimal data concerning the implant status should be acquired by telephone.

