- ❖ **Revision:** Binary indicator variable for presence of revision
- ❖ **Adverse event:** Binary indicator for whether a patient experiences at least one adverse event.
- ❖ **Scores (HHS and WOMAC from HOOS):** The global scores or scores under each dimension of the questionnaire under consideration will be determined per specific scoring instructions for each questionnaire.
 - ❖ Harris Hip Score (HHS)
 - ❖ Algorithms used for scoring each of the 10 items (components) of the HHS as well as the domains (pain, function, AoD and ROM) of the HHS and total HHS are presented below:
 - ❖

CONFIDENTIAL AND PROPRIETARY

This document contains information that is confidential and proprietary to Smith & Nephew PLC and Smith & Nephew, Inc. and is intended for use only by Smith+Nephew and its manufacturer. It shall not be reproduced or copied in whole or in part, nor shall the contents be disclosed by any means without prior written permission from Smith+Nephew, nor shall anyone make any use of it that is contrary to the expressed or implied wishes of Smith+Nephew.

Statistical Analysis Plan

Multicenter Clinical Observation Using the Cementless Version of the
POLARSTEM™

Number: D10070
ST: 1133
Version: 1.0, 30-Nov-2021
Page: 11 of 19

Harris Hip Score (HHS) scores per item and domain			
Item	Original Response	Likely scores per Item	Domains (Range of Scores)
Pain	None or ignores it	44	Pain Domain (0 to 44)
	Slight, minimal, no compromise in activities	40	
	Mild pain, no effect on average activities, rarely moderate pain with unusual activity; may take aspirin	30	
	Moderate pain; tolerable but makes concessions to pain. Some limitation of ordinary activity or work. May require occasional pain medication stronger than aspirin	20	
	Marked pain, serious limitation of activities	10	
	Totally disabled, crippled, pain in bed, bedridden	0	
Limp	None	11	Function Domain (0 to 47) {Sum of all items within subdomain}
	Slight	8	
	Moderate	5	
	Severe	0	
Support	None	11	
	Single cane for long walks	7	
	Single cane most of the time	5	
	One crutch	3	
	Two canes	2	
	Two crutches or not able to walk	0	
Distance walked	Unlimited	11	
	Six blocks	8	
	Two or three blocks	5	
	Indoors only	2	
	Bed and chair only	0	
Sitting	Comfortably in ordinary chair	5	
	On a high chair for 30 minutes	3	
	Unable to sit comfortably in any chair	0	

CONFIDENTIAL AND PROPRIETARY

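### Postoperative adverse events over 10 years are summarised only as crude percentages; read as 10-year risks, these are expected to be too low to the extent that loss to follow-up is not due to death

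*SAP*

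**What the plan says.** SAP 5.4 has two safety endpoints, and SAP 7.13 gives the analysis of each.

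- **Up to discharge:** "Intra- and perioperative implant-related “Adverse Events” (AE) and complications until discharge will be summarised".
- **Long term:** under "Postoperative AE up to 10 years after the surgery", all events are classified by seriousness and by relationship to the device and "given by frequency and percentages". No other method is named.

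SAP 7.4 defines the derived adverse event variable as follows: "Binary indicator for whether a patient experiences at least one adverse event". It carries no date and no time at risk. SAP 7.2 assigns every safety analysis to the Safety Population, which is all subjects who received study treatment.

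Three places show that follow-up will be unequal.

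- Protocol 2.2 says that over 10 years "a drop-out rate of 30% should be considered".
- SAP 7.4, under Completed Subject, says "This study has been terminated early" and counts as completers those who had their 10-year visit before termination. It gives neither the date nor the number of patients cut short.
- Protocol 3.4 says "Complications and adverse events are noted at each follow-up interval". Patients who do not attend are telephoned if possible, and the minimum to be obtained is implant status, not adverse events.

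Revision is treated differently. SAP 7.3 censors lost patients in the survival analysis, and SAP 7.10 gives Kaplan-Meier estimates with 95% confidence intervals at 3 months and 1, 3, 5 and 10 years.

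**The concern.** A patient lost in year 2 stays in the denominator of an ever/never percentage and counts as event-free for eight years in which nobody looked. The SAP recognises this problem for revision and handles it by censoring. It makes no such allowance for postoperative adverse events in the same patients over the same period.

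The study has no control arm, so no between-group comparison exists in which similar loss might partly cancel. The percentage itself is what a reader will take away about non-revision events. If it is taken as a 10-year risk, late serious or device-related events may look rarer than they are. Telephone contact does not close the gap, because a call may settle implant status and leave adverse events unasked.

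**Working it through.** **Inputs.** From the documents: 30% drop-out over 10 years (Protocol 2.2, a planning figure) and 225 patients implanted (SAP 7.15). The documents give no adverse event rate, no event timing, no drop-out timing, no observed loss and no share of loss due to death. All of these are assumptions below.

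**The plan's own figure.** Only the sample size in Protocol 2.2 uses the drop-out rate. 100/(1 − 0.30) = 142.9, so 143 against the stated 150; 150 × 0.70 = 105. The stated number is slightly generous, and the difference does not bear on this point. There is no planned adverse event figure to reproduce.

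**Patients concerned.** 225 × 0.30 = 67.5, so about 67 patients would lack full follow-up at the planned drop-out.

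**Constant hazards, loss non-fatal and non-informative.** With true 10-year risk p, event hazard h = −ln(1 − p)/10 and loss hazard c = −ln(0.70)/10 = 0.03567, the expected crude proportion is

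crude = h/(h + c) × (1 − exp(−10(h + c))).

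- p = 10%: h = 0.01054; 0.2280 × (1 − 0.90 × 0.70) = 0.2280 × 0.37 = 8.44%; ratio 0.844.
- p = 20%: h = 0.02231; 0.3849 × (1 − 0.80 × 0.70) = 0.3849 × 0.44 = 16.9%; ratio 0.847.
- p = 5% gives 4.2% and p = 40% gives 34.2%; ratios 0.842 and 0.854.

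A simulation with 225 patients per replicate at p = 20% also gave 16.9%.

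**Other timing patterns.** In general, crude = ∫G(t)dF(t), where F is the cumulative incidence of a first event and G the probability of still being followed, with G(10) = 0.70. Ratios of crude to true risk at p = 20%:

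| Event timing | Loss at constant hazard | Loss linear | All loss in year 1 | Loss only after year 5 |
|---|---|---|---|---|
| Constant hazard | 0.847 | 0.856 | 0.717 | 0.930 |
| Half in first 3 months, rest spread evenly | 0.916 | 0.921 | 0.836 | 0.962 |
| Late (F rising with t²) | 0.791 | 0.800 | 0.701 | 0.875 |

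**Early termination.** If, in addition, 10% to 50% of those still followed are cut off at year 7 or year 9 (assumed), the constant-hazard ratio at p = 20% falls from 0.847 to between 0.74 and 0.84.

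**Death as part of the 30%.** Split c into a death hazard μ = wc and a non-fatal loss hazard (1 − w)c. The target is then the cumulative incidence, h/(h + μ) × (1 − exp(−10(h + μ))). The crude value stays at 16.9%. With h set as for p = 20%:

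| Share of loss that is death (w) | True cumulative incidence | Crude/true | 1 − Kaplan-Meier |
|---|---|---|---|
| 0 | 20.0% | 0.85 | 20% |
| 0.25 | 19.2% | 0.88 | 20% |
| 0.50 | 18.4% | 0.92 | 20% |
| 0.75 | 17.6% | 0.96 | 20% |
| 1 | 16.9% | 1.00 | 20% |

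Death removes the bias in the crude figure in proportion to its share. It also makes 1 − Kaplan-Meier too high.

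**The case against.** A reader might infer that the study's safety results as a whole are biased low. The documents do not support that. Stem revision for any reason, the main device failure, is planned by Kaplan-Meier with censoring; a simple proportion is only a fallback if the data do not allow it (SAP 7.1). Revisions are also tabulated or listed by type (SAP 7.10). Events up to discharge are complete before later drop-out can matter.

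A reader might also infer a fixed understatement of about 16%. That does not follow either. The 30% is a planning allowance, the effect of early termination cannot be sized from what is given, and some loss over 10 years in patients aged up to 75 is likely to be death, for which counting the later years as event-free is correct.

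A crude percentage is also valid as an observed proportion, and SAP 7.13 does not call it a 10-year risk. The denominator is inferred from SAP 7.2, and the table shells are not available. SAP 7.6 reports patients due, terminated, expected and present at each visit, and SAP 7.3 promises an assessment of informative missingness.

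These points limit the scope and the certainty, and all of them stand. They do not remove the gap. No section adjusts the adverse event percentages, and because events are not tabulated by interval, a reader cannot combine them with the disposition table.

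**Conclusion.** The point holds for postoperative adverse events after discharge, other than revision. The plan offers only crude percentages of everyone treated, under planned loss and a stated early end. Read as 10-year risks, they are expected to be low to the extent that loss is not death.

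The size is unknown. With 30% non-fatal, non-informative loss, the ratio of crude to true risk is about 0.84 under constant hazards and 0.70 to 0.96 across the assumed timing patterns. With a 20% risk and constant hazards, it is 0.92 if half the loss is death and 1.00 if all of it is. If loss depends on patients' condition, neither the crude figure nor a censored estimate is free of bias, and the direction cannot be fixed from the documents. This is a worthwhile reporting improvement, not a flaw that invalidates the planned table.

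**What to change.** Keep the crude table in SAP 7.13, labelled as the observed proportion. For serious and for device-related postoperative events, add:

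- events per 100 patient-years;
- cumulative incidence of first event at 3 months and 1, 3, 5 and 10 years with 95% confidence intervals and numbers at risk, censoring at the last adverse event assessment and treating death as a competing event (not 1 minus Kaplan-Meier).

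The censoring date should be the last adverse event assessment, not the last contact, because a telephone call may have covered implant status only.

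Protocol 3.4 records events by follow-up interval, and the documents do not show that onset dates were collected. If they were not, report percentages per interval, with the number assessed in that interval as denominator.

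The cost is one or two extra tables, with no new data collection if the interval version is used. The 10-year adverse event figures would probably look slightly less favourable.
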